8.5 Changes to the protocol and informed consent form

Study procedures will not be changed without the mutual agreement of the PI and AstraZeneca.

Clinical Study Protocol
Drug Substance Dapagliflozin/metformin
Study Code D1691C00007
Edition Number 1
Date [REDACTED]

If there are any substantial changes to the study protocol, then these changes will be documented in a study protocol amendment and where required in a new version of the study protocol (Revised CSP).

The amendment is to be approved by the relevant EC and if applicable, also the national regulatory authority approval, before implementation. Local requirements are to be followed for revised protocols.

AstraZeneca will distribute any subsequent amendments and new versions of the protocol to each PI(s). For distribution to EC see Section 8.3.

If a protocol amendment requires a change to a centre's ICF, AstraZeneca and the centre's EC are to approve the revised ICF before the revised form is used.

If local regulations require, any administrative change will be communicated to or approved by each EC.

8.6 Audits and inspections

Authorised representatives of AstraZeneca, a regulatory authority, or an EC may perform audits or inspections at the centre, including source data verification. The purpose of an audit or inspection is to systematically and independently examine all study-related activities and documents, to determine whether these activities were conducted, and data were recorded, analysed, and accurately reported according to the protocol, GCP, ICH guidelines, and any applicable regulatory requirements. The Investigator will contact AstraZeneca immediately if contacted by a regulatory agency about an inspection at the centre.

9. STUDY MANAGEMENT

Quintiles will be managing the study on behalf of AstraZeneca.

9.1 Pre-study activities

Before the first healthy volunteer is entered into the study, it is necessary for a representative of AstraZeneca to visit the investigational study site to:

- Determine the adequacy of the facilities
- Determine availability of appropriate healthy volunteers for the study
- Discuss with the Investigator(s) (and other personnel involved with the study) their responsibilities with regard to protocol adherence, and the responsibilities of AstraZeneca or its representatives. This will be documented in a CSA between AstraZeneca and the Investigator.

9.2 Training of study site personnel

Before the first healthy volunteer is entered into the study, an AstraZeneca representative will review and discuss the requirements of the CSP and related documents with the investigational staff and also train them in any study specific procedures and system(s) utilised.

The PI will ensure that appropriate training relevant to the study is given to all of these staff, and that any new information relevant to the performance of this study is forwarded to the staff involved.

The PI will maintain a record of all individuals involved in the study (medical, nursing and other staff).

9.3 Monitoring of the study

During the study, an AstraZeneca/Quintiles representative will have regular contacts with the study site, including visits to:

- Provide information and support to the Investigator(s)
- Confirm that facilities remain acceptable
- Confirm that the investigational team is adhering to the protocol, that data are being accurately and timely recorded in the CRFs, that biological samples are handled in accordance with the Laboratory Manual and that study drug accountability checks are being performed
- Perform source data verification (a comparison of the data in the CRFs with the healthy volunteer's medical records at the hospital or practice, and other records relevant to the study) including verification of informed consent of participating healthy volunteers. This will require direct access to all original records for each subject (eg, clinic charts)
- Ensure withdrawal of informed consent to the use of the healthy volunteer's biological samples is reported and biological samples are identified and disposed of/destroyed accordingly, and the action is documented, and reported to the volunteer.

The AstraZeneca representative will be available between visits if the Investigator(s) or other staff at the centre needs information and advice about the study conduct.

9.3.1 Source data

The location of data identified as source will be provided in a source data identification document provided by Quintiles.

Clinical Study Protocol
Drug Substance Dapagliflozin/metformin
Study Code D1691C00007
Edition Number 1
Date [REDACTED]

9.4 Study agreements

The PI at the centre should comply with all the terms, conditions, and obligations of the CSA, or equivalent, for this study. In the event of any inconsistency between this CSP and the CSA, the terms of CSP shall prevail with respect to the conduct of the study and the treatment of volunteers and in all other respects, not relating to study conduct or treatment of volunteers, the terms of the CSA shall prevail.

Agreements between AstraZeneca and Quintiles should be in place before any study-related procedures can take place, or subjects are enrolled.

9.4.1 Archiving of study documents

The Investigator follows the principles outlined in the CSA.

9.5 Study timetable and end of study

The end of the study is defined as 'the last visit of the last healthy volunteer undergoing the study'.

The study is expected to start in Q2 [REDACTED] and to end by Q3 [REDACTED].

The study may be terminated at individual centres if the study procedures are not being performed according to GCP or if recruitment is slow. AstraZeneca may also terminate the entire study prematurely if concerns for safety arise within this study or in any other study with dapagliflozin or metformin.

10. DATA MANAGEMENT BY QUINTILES

Data management will be performed by Quintiles Ltd, [REDACTED].

The data in this study will be collected using paper CRFs.

When the completed paper CRFs have been scanned and indexed, the data are entered into the study database and proofread.

The data collected through third party sources will be obtained and reconciled against study data.

Adverse events and medical/surgical history will be classified according to the terminology of the latest version the Medical Dictionary for Regulatory Activities (MedDRA). Medications will be classified according to the AstraZeneca Drug Dictionary. All coding will be performed by Quintiles Ltd, [REDACTED].

Data queries will be raised for inconsistent, impossible or missing data. All entries to the study database will be available in an audit trail.

Clinical Study Protocol
Drug Substance Dapagliflozin/metformin
Study Code D1691C00007
Edition Number 1
Date [REDACTED]

The data will be validated as defined in the Data Management Plan. Quality control procedures will be applied to each stage of data handling to ensure that all data are reliable and have been processed correctly.

When all data have been coded, validated and signed the database will be locked.

Data associated with biological samples will be transferred to laboratories internal or external to AstraZeneca.

11. EVALUATION AND CALCULATION OF VARIABLES BY QUINTILES

11.1 Calculation or derivation of efficacy variable(s)

Not applicable.

11.2 Calculation or derivation of safety variable(s)

Adverse events will be collected for each healthy volunteer from the first administration of IMP (Day 1, Visit 2) until the follow-up visit (Visit 6). Serious AEs will be collected from when informed consent is obtained (Visit 1) until the follow-up visit (Visit 6). Summary statistics will be presented for the continuous safety variables.

11.2.1 Other significant adverse events (OAE)

During the evaluation of the AE data, an AstraZeneca medically qualified expert will review the list of AEs that were not reported as SAEs and discontinuation of IMP due to AEs. Based on the expert's judgement, significant AEs of particular clinical importance may, after consultation with the CPA Physician, be considered OAEs and reported as such in the CSR. A similar review of laboratory tests, vital signs and ECG data will be performed for identification of OAEs.

Examples of these are marked haematological and other laboratory abnormalities, and certain events that lead to intervention (other than those already classified as serious), dose reduction or significant additional treatment.

11.3 Calculation or derivation of patient reported outcome variables

Not applicable.

11.4 Calculation or derivation of pharmacokinetic variables

The PK analyses will be performed at Quintiles Inc, [REDACTED]. Quintiles Standard Operating Procedures (SOPs) and Work Instructions will be used as the default methodology if not otherwise specified. The actual sampling times will be used in the PK calculations. PK parameters will be derived using noncompartmental methods with WinNonlin® Professional Version 5.2, or higher, (Pharsight Corp., [REDACTED]),

Clinical Study Protocol
Drug Substance Dapagliflozin/metformin
Study Code D1691C00007
Edition Number 1
Date [REDACTED]

[REDACTED]). All PK computations will be performed using WinNonlin Professional 5.2, or higher; or SAS® Version 9.1, or higher (SAS Institute, Inc., [REDACTED], [REDACTED]). Graphics may be prepared with SAS Version 9.1, or higher; or SigmaPlot® 9.0, or higher (Systat Software, Inc., [REDACTED], [REDACTED]).

Any anomalous concentration values observed at the predose time point shall be identified in the PK analysis review documentation with a description of how the value was treated. If the anomalous predose concentration value is greater than 5% of the maximum observed concentration (C_{max}) in the profile, PK parameters for the profile will not be reported.

If data permits, the following single dose PK parameters will be determined for dapagliflozin and metformin:

C_{max}	Observed maximum analyte concentration, taken directly from the individual concentration-time curve.
t_{max}	Time to reach maximum analyte concentration, taken directly from the individual concentration-time curve.
t_{last}	Time of last quantifiable analyte concentration.
λ_z	Terminal rate constant, estimated by log-linear least squares regression of the terminal part of the concentration-time curve.
$t_{1/2z}$	Terminal half-life, estimated by $(\ln 2)/\lambda_z$.
$AUC_{(0-t)}$	Area under the plasma concentration-curve from time zero to the time of last quantifiable analyte concentration, calculated by linear up/log down trapezoidal summation.
AUC	Area under the plasma concentration-time curve from time zero extrapolated to infinity. AUC is estimated by $AUC_{(0-t)} + C_{last}/\lambda_z$ where C_{last} is the last observed quantifiable analyte concentration.
$\%C_0/C_{max}$	Percent of predose concentration relative to C_{max}
$\%AUC_{(0-t)}/AUC$	Percent of the area measured by $AUC_{(0-t)}$ relative to the extrapolated total AUC.

Additional calculations may be performed at the discretion of the PK scientist as appropriate.

The following PK diagnostic parameters will be calculated and listed but not summarised:

- The t_{lower} and t_{upper} of the log-linear regression to determine $t_{1/2z}$.
- Number of data points ($t_{1/2}$, N) included in the log-linear regression analysis.
- Goodness of fit statistic, R-Squared, for calculation of λ_z [Rsq].
- Percentage of AUC obtained by extrapolation ($\%AUC_{ex}$).

Clinical Study Protocol
Drug Substance Dapagliflozin/metformin
Study Code D1691C00007
Edition Number 1
Date [REDACTED]

Additional PK parameters may be calculated if deemed appropriate.

All concentration and PK parameters will be presented according to Health Canada’s Guidance Document, “Conduct and Analysis of Bioavailability and Bioequivalence Studies - Part A.” (For details, refer to: http://www.hc-sc.gc.ca/dhp-mpps/prodpharma/applic-demande/guide-ld/bio/gd_cbs_etc_ld-eng.php)

Assessment		Sample volume (mL)	No. of samples	Total volume (mL)
Safety	Clinical chemistry	4	6	24
	Haematology	4	6	24
	Coagulation	3	1	3
	Serology	4	1	4
Endocrinology	FSH ^a	4	1	4
Pharmacokinetic		6	88	528
Total				583 (587)

Comment [sw1]: 587 is correct. What does 583 represent? Which value can vary?

11.5 Calculation or derivation of pharmacodynamic variable(s)

Not applicable.

11.6 Calculation or derivation of pharmacogenetic variables

Not applicable.

11.7 Calculation or derivation of health economic variables

Not applicable.

12. STATISTICAL METHODS AND SAMPLE SIZE DETERMINATION BY QUINTILES

12.1 Description of analysis sets

12.1.1 Safety analysis set

All healthy volunteers who received at least one dose of randomised IMP, and for whom any postdose data are available will be included in the safety population. Throughout the safety results sections, erroneously treated healthy volunteers (eg, those randomised to treatment A but actually given Treatment B) will be accounted for in the actual treatment group.

12.1.2 Pharmacokinetic analysis set

The PK analysis set will include all healthy volunteers who received at least 1 dose of IMP and who have sufficient PK data to evaluate any of the primary outcome variables (AUC, $AUC_{(0-t)}$ or C_{max}) and have no major protocol deviations or violations affecting the integrity of the PK data. Data from healthy volunteers who experience emesis at or before 2 times median t_{max} will only be listed and not be included in any statistical analysis.

A strategy for dealing with data affected by protocol violations and deviations will be agreed by the study team physician, pharmacokineticist, and statistician, prior to clean file and code break. Healthy volunteers will be analysed according to the treatment they actually received.

12.2 Methods of statistical analyses

The statistical analyses will be performed by Quintiles Inc, [REDACTED] by using SAS, version 9.1 or later. Quintiles SOPs and Work Instructions will be used as the default methodology if not otherwise specified.

Data will be presented by treatment. Missing data will result in a reduced sample size for that parameter. No action will be taken to handle missing data.

A healthy volunteer who withdraws prior to the last planned observation in a study period will be included in the analyses up to the time of discontinuation.

Plasma concentrations and derived PK parameters will be reported to 3 significant figures; standard deviation will be reported to 4 significant figures and CVs will be presented to 1 decimal place. For all other data types, mean, median, minimum and maximum values will be reported to the same degree of precision as the raw data and the standard deviation will be reported to one further degree of precision. Percentage frequencies will generally be presented to the nearest integer. For derived data, rounding should be applied after calculations have been performed.

The primary objectives of this study are to demonstrate bioequivalence of a dapagliflozin/metformin (5 mg/850 mg) IR FDC tablet relative to 5-mg dapagliflozin and 850-mg Glucophage[®] (marketed in Canada by SA) tablets administered together in the fasted state and to demonstrate the bioequivalence of a dapagliflozin/metformin (5 mg/850 mg) IR FDC tablet relative to 5-mg dapagliflozin and 850-mg Glucophage[®] (marketed in Canada by SA) tablets administered together in the fed state. These analyses will be performed using the nominal drug dose and corrected for the measured potency of the administered formulations.

In the fasted condition, point estimates and 90% confidence intervals for C_{max} , $AUC_{(0-t)}$, and AUC will be calculated for the Treatment B to Treatment A ratios of geometric means of dapagliflozin and metformin using a linear mixed effect model. In the fed condition, point estimates and 90% confidence intervals for C_{max} , $AUC_{(0-t)}$, and AUC will be calculated for the Treatment D to Treatment C ratios of geometric means of dapagliflozin and metformin using a linear mixed effect model. These estimates will be constructed from the results of fitting the linear mixed effect models for log-transformed data with treatment sequence and period as

Clinical Study Protocol
Drug Substance Dapagliflozin/metformin
Study Code D1691C00007
Edition Number 1
Date [REDACTED]

fixed effects and subject within sequence as a random effect. All statistical comparisons will be made from this same model. Point estimates of the ratios and their confidence intervals will then be transformed back to original scale in order to give point estimates for the ratios of geometric means and their confidence intervals.

Bioequivalence will be concluded if the test-to-reference ratios of geometric means are contained within 0.80 to 1.25 for dapagliflozin and metformin AUC, AUC_(0-t) and C_{max}. No adjustments will be made for multiplicity.

To look at fed versus fasted for the dapagliflozin/ metformin (5 mg/850 mg) IR FDC tablet, point estimates and 90% confidence intervals for C_{max}, AUC_(0-t), and AUC will be calculated for the Treatment D to Treatment B ratios of geometric means of dapagliflozin and for metformin using a linear mixed effect model. These estimates will be constructed from the results of fitting the linear mixed effect models for log-transformed data with treatment and period as fixed effects and subject within sequence as a random effect. Point estimates of the differences and their confidence intervals will then be transformed back to original scale in order to give point estimates for ratios of geometric means in the original scale.

A secondary analysis will be performed if the C₀/C_{max} ratio is greater than 5% and/or the AUC_(0-t)/AUC ratio is less than 80%. Any volunteers who fall within either category will be excluded from the dataset, and a secondary analysis will be repeated.

No treatment comparisons will be made between Treatment A and Treatments C and D; nor between Treatment B and Treatment C.

The bioequivalence analyses will (if applicable) also be performed on the PK parameters corrected for the actual drug content of each of the formulations (potency-corrected analysis). See below examples of the methods of calculating the AUC, AUC_(0-t) and C_{max} ratio estimates and their confidence limits, based on data corrected for measured content. The whole analysis need not be repeated; but only the corrected estimates need to be given.

Table 3 Estimates based on correction for measured content (example)

	Test Formulation	Reference Formulation
Lot number	EX109	40904
Expiry date	06/89	05/89
Date of analysis	01/04/88	01/04/88
Measured content (% of label claim)	95.4	99.3
Correction factors		
- raw scale-multiply	1.0482	1.0070
- log scale-add	0.0471	0.0070

AUC ratio and C_{max} ratio – calculations (example)

Based on measured contents in the example above, the following factor is obtained:

$\ln(99.3/95.4) = 0.04$, which is to be added to the estimates on the ln scale.

Therefore:

$$\text{AUC ratio} = e^{(-0.13 + 0.04)} * 100\% = 91\%$$

$$\text{Lower limit} = 100 * e^{(-0.13 + 0.04 - 1.761 * 0.0955)} = 77\%$$

$$\text{Upper limit} = 100 * e^{(-0.13 + 0.04 + 1.761 * 0.0955)} = 108\%$$

$$\text{C}_{\text{max}} \text{ ratio} = e^{(-0.21 + 0.04)} = 84\%$$

$$\text{Lower limit} = 100 * e^{(-0.21 + 0.04 - 1.761 * 0.1600)} = 64\%$$

$$\text{Upper limit} = 100 * e^{(-0.21 + 0.04 + 1.761 * 0.1600)} = 112\%$$

A listing of PK blood sample collection times as well as derived sampling time deviations will be provided. A listing of all concentration-time data for each treatment will be presented. Pharmacokinetic variables (dapagliflozin and metformin plasma concentrations and PK parameters) will be summarized by treatment using appropriate descriptive statistics, eg n, arithmetic mean, standard deviation (SD), geometric mean, geometric coefficient of variation (CV%), minimum (min), median, maximum (max). The geometric mean is calculated as the exponential of the arithmetic mean calculated from data on a log scale. The CV% is calculated as $100 \cdot \sqrt{(\exp(s^2) - 1)}$ where s is the SD of the data on a log scale. For t_{max} and t_{last} only n, median, min and max will be used.

Plasma concentrations that are below the LLOQ will be handled as follows:

- At a time point where at least 1 value is above LLOQ, but less than 50% values are LLOQ, all values below LLOQ are set to LLOQ and a mean (arithmetic and geometric) value and SD and CV (coefficient of variation) are calculated.
- At a time point where more than half of the observations are below LLOQ only individual values are reported; mean, SD, geometric mean and CV% will be set to NQ. The minimum (min) value and the median are set to less than LLOQ.
- If all values are below LLOQ at any time point no descriptive statistics are calculated for that time point. Write NA (not applicable) in the field for standard deviation and CV% and write less than LLOQ in fields for mean, geometric mean, min, median and max in the table.
- The number of observations greater than LLOQ [number of observations above LLOQ (N>LLOQ)] will be reported in the table.

Quintiles global SOPs will be followed for the rounding conventions.

Clinical Study Protocol
Drug Substance Dapagliflozin/metformin
Study Code D1691C00007
Edition Number 1
Date [REDACTED]

Figures of arithmetic mean concentration-time data will be presented on linear and semi-logarithmic scales by treatment. Individual concentration-time data will be graphically presented on linear and semi-logarithmic scales, with the semi-log plot presenting the regression line from which λ_z was estimated. Graphical presentations of PK data may be added at the discretion of the PK scientist.

Frequency distributions of gender and race will be tabulated by treatment. Summary statistics for age, body weight, height, and BMI will be tabulated by treatment.

All recorded AEs will be listed and tabulated by system organ class, preferred term and formulation. Vital signs and clinical laboratory test results will be listed and summarized by formulation. Any significant physical examination findings, ECG results, and clinical laboratory results will be listed.

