The analysis will be performed using the nominal drug dose and corrected for the measured potency of the administered formulations. Point estimates and 90% confidence intervals for C_{\max} , $AUC_{(0-t)}$, and AUC will be calculated for the Test to Reference ratios of geometric means of dapagliflozin and metformin using a linear mixed effect model. The reference and test treatments are defined as Treatments A and B, respectively, for comparisons within the fasted state, and as Treatments C and D, respectively, for comparisons within the fed state. These estimates will be constructed from the results of fitting the linear mixed effect models for log-transformed data with treatment sequence and period as fixed effects and subject within sequence as a random effect. Point estimates of the ratios and their confidence intervals will then be transformed back to original scale in order to give point estimates for the ratios of geometric means and their confidence intervals. As per guidelines from Health Canada, bioequivalence will be demonstrated if the 90% confidence interval of the ratio of geometric means of AUC and C_{\max} of the test to reference is within 80% to 125%.

Effect of food for the dapagliflozin/metformin (5 mg/850 mg) IR FDC tablet will be analysed with a similar model as described above.

TABLE OF CONTENTS

PAGE

TITLE PAGE	1
PROTOCOL SYNOPSIS	2
TABLE OF CONTENTS	6
LIST OF ABBREVIATIONS AND DEFINITION OF TERMS	10
1. INTRODUCTION	13
1.1 Background	13
1.2 Research hypotheses.....	13
1.3 Rationale for conducting this study	14
1.4 Benefit/risk and ethical assessment	15
2. STUDY OBJECTIVES	16
2.1 Primary objectives	16
2.2 Secondary objectives	16
3. STUDY PLAN AND PROCEDURES	17
3.1 Overall study design and flow chart	17
3.2 Rationale for study design, doses and control groups	21
4. SUBJECT SELECTION CRITERIA.....	21
4.1 Inclusion criteria.....	21
4.2 Exclusion criteria.....	22
5. STUDY CONDUCT	24
5.1 Restrictions during the study	24
5.2 Subject enrolment and randomisation.....	25
5.2.1 Procedures for randomisation	26
5.3 Procedures for handling subjects incorrectly enrolled or randomised.....	26
5.4 Blinding and procedures for unblinding the study	26
5.5 Treatments.....	26
5.5.1 Identity of investigational medicinal product(s)	26
5.5.2 Doses and treatment regimens	26
5.5.3 Additional study drug	27
5.5.4 Labelling	27
5.5.5 Storage	28

5.6	Concomitant and post-study treatment(s)	28
5.7	Treatment compliance	28
5.7.1	Accountability	29

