The individual tablets of metformin hydrochloride (Glucophage[®]) were manufactured by Merck. The IR metformin tablet to be used in the present study is manufactured by Merck and marketed by SA. Health Canada requires that bioequivalence be demonstrated to the marketed product in single dose cross-over comparative bioavailability studies, so this study is being conducted in order to meet this requirement. The criteria for demonstrating bioequivalence as per the guidelines are that the 90% confidence interval of the relative mean AUC of the test to reference product should be within 80% to 125%, and the relative mean measured C_{\max} of the test to reference product should be between 80% and 125%. There are 4 different FDC tablets: 2.5 mg/850 mg; 2.5 mg/1000 mg; 5 mg/850 mg; and 5 mg/1000 mg of dapagliflozin/metformin, respectively. The tablet to be utilised in this study is the dapagliflozin/metformin 5 mg/850 mg IR FDC tablet. Normally bioequivalence studies are performed with the highest dose, as the bioequivalence issues are most likely to be demonstrated with the highest dose in compounds with linear pharmacokinetics (PK), hence

the choice of the 5-mg dose for dapagliflozin. Metformin, however, has dose-related absorption with diminished absorption with higher doses. Therefore, the lower dose is more sensitive to the performance of the formulation, so the 850-mg dose of metformin is to be studied. For further details on the rationale for dose selection, refer to Section 3.2.

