12.3 Determination of sample size

Dapagliflozin

Assume there is no difference between the bioavailabilities of dapagliflozin from the 5-mg dapagliflozin/850 mg metformin FDC tablet versus dapagliflozin from co-administration of a 5-mg dapagliflozin tablet and an 850-mg Glucophage (marketed in Canada by SA) tablet under both fasted and fed conditions,

From Study D1691C00002, C_{max} , $AUC_{(0-t)}$, and AUC are log normally distributed with intra-subject standard deviations of 0.286, 0.081, and 0.093 for $\log(C_{max})$, $\log[AUC_{(0-t)}]$, and $\log[AUC]$, respectively.

Using a 90% power and a 2-sided alpha of 5%, there will need to be 3 healthy volunteers per treatment sequence, 12 healthy volunteers total, to conclude bioequivalence with respect to $AUC_{(0-t)}$ and AUC.

Using a 95% power and a 2-sided alpha of 5%, there will need to be 3 healthy volunteers per treatment sequence, 12 healthy volunteers total, to conclude bioequivalence with respect to $AUC_{(0-t)}$ and AUC.

If there is a 5% difference between the treatments, using a 90% power and a 2-sided alpha of 5%, there will need to be 3 healthy volunteers per treatment sequence, 12 healthy volunteers total, to conclude bioequivalence with respect to $AUC_{(0-t)}$ and AUC.

Assuming there is no difference in the C_{max} between the 2 treatments, there will need to be 7 healthy volunteers per treatment sequence, 28 healthy volunteers total, to have a 95% probability of the measured C_{max} of the test to reference product to be between 80% and 125%.

Clinical Study Protocol
Drug Substance Dapagliflozin/metformin
Study Code D1691C00007
Edition Number 1
Date [REDACTED]

If there is a 5% difference between treatments for C_{\max} , there will need to be 8 healthy volunteers per treatment sequence, 32 healthy volunteers total, to have a 95% probability of the measured C_{\max} of the test to reference product to be between 80% and 125%.

Metformin

Assume there is no difference between the bioavailabilities of metformin from the 5 mg dapagliflozin/850 mg metformin FDC tablet versus dapagliflozin from coadministration of a 5-mg dapagliflozin tablet and an 850-mg Glucophage (marketed in Canada by SA) tablet under both fasted and fed conditions.

From saxagliptin Study CV181081, C_{\max} , $AUC_{(0-t)}$, and AUC are log normally distributed with intra-subject standard deviations of 0.220, 0.180, and 0.174 for $\log(C_{\max})$, $\log[AUC_{(0-t)}]$, and $\log[AUC]$, respectively.

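### The protocol states three different bioequivalence rules, and Section 12.2 as written decides on point ratios without the 90% confidence intervals it calculates

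*Protocol*

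**What the plan says.** The protocol gives the criterion for its primary objectives in three places.

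- **Synopsis, Statistical methods:** "bioequivalence will be demonstrated if the 90% confidence interval of the ratio of geometric means of AUC and" Cmax lies within 80% to 125%. AUC(0-t) is not in this sentence, although the Synopsis lists it as a primary variable.
- **Section 1.3:** for AUC, "the 90% confidence interval of the relative mean AUC of the test to reference product should be within 80% to 125" percent. For Cmax, it is the relative mean measured value that "of the test to reference product should be between 80% and 125" percent, with no interval.
- **Section 12.2:** "Bioequivalence will be concluded if the test-to-reference ratios of geometric means are contained within 0.80 to 1.25", applied to AUC, AUC(0-t) and Cmax of dapagliflozin and metformin. No interval appears in the sentence, although the same section has just planned them: "In the fasted condition, point estimates and 90% confidence intervals for" all three parameters, and likewise for the fed state.

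Section 12.3 follows the split in Section 1.3. AUC and AUC(0-t) are sized with an alpha and a power for concluding bioequivalence. Cmax is sized for a 95% probability that the measured ratio lies between 80% and 125%.

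**The concern.** A bioequivalence study stands or falls on one decision rule, and here the rule depends on the section followed. A point-estimate rule does not control the risk of accepting a product that lies on the equivalence limit. The 90% interval rule holds that risk at 5% per parameter. For AUC, Section 12.2 alone omits the interval. For Cmax, the Synopsis stands on one side and Sections 1.3 and 12.3 on the other. A later analysis plan cannot satisfy all of these, so the choice could end up being made after results are known.

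**Working it through.** **Inputs.** Section 12.3 gives, for dapagliflozin, "intra-subject standard deviations of 0.286, 0.081, and 0.093" (log Cmax, log AUC(0-t), log AUC). For metformin it gives 0.220, 0.180 and 0.174. Planned completers: 32. Limits: ln 0.80 = −0.2231 and ln 1.25 = 0.2231.

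**The plan's own Cmax figure.** Section 12.3 needs 32 completers for dapagliflozin Cmax with a 5% difference. With SE = SD·√(4/N) = 0.286·√(4/32) = 0.1011 and a true ratio of 1.05 (ln = 0.0488), the probability that the measured ratio is in range is Φ(0.1744/0.1011) − Φ(−0.2719/0.1011) = 0.954. At N = 28 it is about 0.94, so 32 is reproduced. The same formula gives the other three stated Cmax figures (28, 16 and 20). Cmax was therefore sized on the point ratio.

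**Pass probability at the limit.** For a within-subject SD in a four-period crossover the usual SE is SD·√(2/N). For dapagliflozin Cmax this is 0.286·√(2/32) = 0.0715. With 3·32 − 6 = 90 degrees of freedom, t = 1.662 and the 90% interval half-width is 1.662 × 0.0715 = 0.119. The interval rule then needs an observed ratio between exp(−0.2231 + 0.119) = 0.90 and exp(0.2231 − 0.119) = 1.11. The point rule accepts 0.80 to 1.25.

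- True ratio 0.80 or 1.25: point rule 50.0%, interval rule 5.0%. This holds for all six analyte–parameter pairs at the protocol's SDs.
- The Section 1.3 rule gives 5% for AUC and 50% for Cmax.
- True ratio 0.75, dapagliflozin Cmax: point rule 1 − Φ(0.0645/0.0715) = 18%, interval rule 0.5%. This is the most variable parameter. The point rule passes 7.6% for metformin AUC(0-t) (SE 0.045) and 0.3% for dapagliflozin AUC (SE 0.023).

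**Power at 32 completers under the interval rule, SE = SD·√(2/N).**

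| Parameter | No difference | 5% difference |
|---|---|---|
| Dapagliflozin Cmax | 85% | 76% |
| Metformin Cmax | 98% | 93% |
| AUC and AUC(0-t), either analyte | over 99% | at least 98% |

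Under the point rule, dapagliflozin Cmax passes with probability 99.8% and 99.3%. For 90% power under the interval rule it needs 40 completers with no difference and 48 to 52 with a 5% difference. Maximum enrolment is 40.

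**The protocol's worked example.** The potency example in Section 12.2 is illustrative, not trial data. It shows AUC 91% (77–108%) and Cmax 84% (64–112%). Under 12.2 as written both pass. Under the Synopsis both fail. Under Section 1.3 AUC fails and Cmax passes.

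**The case against.** The strongest reply is that Section 12.2 has merely lost a few words. It calculates 90% intervals for exactly these ratios just before the decision sentence. Section 1.3 describes the 90% criterion as standard when it reports the previous study. Section 12.3 sizes AUC with an alpha and a power, which would be pointless under a point rule. For AUC this is persuasive: a reader might infer that the sponsor has adopted a point-estimate rule for every parameter, and the document as a whole does not support that.

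The reply does not dispose of the matter. If the missing words are supplied, Section 12.2 agrees with the Synopsis but contradicts Sections 1.3 and 12.3 on Cmax. Nor can the document settle which Cmax rule is required, since the Synopsis and Section 1.3 each present their own version as the guideline criterion.

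The absence of AUC(0-t) from the Synopsis and Section 1.3 rules is minor, because Section 1.2, the Synopsis variable list and Section 12.2 all include it.

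**Conclusion.** The contradiction is real and concerns the primary decision criterion, so it must be resolved before data are seen. Its size is about 50% against about 5%, per parameter, at a true ratio on the equivalence limit, with the protocol's SDs and 32 completers.

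Three stronger readings do not hold:

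- A reader might infer that the study carries a 50% risk of a false conclusion. It does not follow: all parameters of both analytes must pass, so the single-parameter figure is only an upper bound.
- A reader might infer that 50% and 5% apply whatever the variability. They do not: with 32 completers, at an SD of 0.6 the interval rule passes only 0.1% at the limit, and at an SD of 1.0 the point rule passes 46%.
- A reader might infer that the study is underpowered. That depends on a Cmax rule not yet settled. Under the rule used in Section 12.3 the stated sample size is reproduced.

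The 85% and 76% rest on SE = SD·√(2/N). Under the larger SE that reproduces the protocol's Cmax sample sizes, SD·√(4/N), they would be 41% and 37%. Section 12.3 should therefore state the SE it uses.

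**What to change.** 1. In Section 12.2, state that bioequivalence requires the 90% confidence intervals of the test-to-reference ratios for AUC and AUC(0-t) to lie within 0.80 to 1.25 for both analytes, judged separately for the fasted and fed states.
2. Choose one rule for Cmax, either the 90% interval or the point ratio, and name it as such.
3. State the rules identically in the Synopsis, Section 1.3 and Section 12.2, with AUC(0-t) included.
4. Make Section 12.3 consistent with the chosen Cmax rule. If the interval rule is chosen, restate power for dapagliflozin Cmax at 32 completers as about 85% with no difference and about 76% with a 5% difference, giving the SD (0.286) and the SE formula.

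Cost: wording changes in four places, with no change to data collection. The interval rule costs almost no power for AUC and AUC(0-t). For Cmax it brings a less favourable stated power, and 90% power for dapagliflozin would need 40 completers with no difference or 48 to 52 with a 5% difference. The sponsor would have to accept the lower power or revisit the enrolment ceiling of 40.
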